7. DISCONTINUATION OF STUDY VACCINATION AND PARTICIPANT DISCONTINUATION/WITHDRAWAL

7.1. Discontinuation of Study Vaccination

Study vaccinations will be withheld for the reasons listed below. These participants must not receive any further doses of study vaccine but should remain on study for follow-up of safety and immunogenicity as indicated in the Schedule of Activities (Section 1.3). Additional unscheduled visits may be performed for safety/reactogenicity reasons, if needed. In case of questions, the investigator is encouraged to contact the sponsor.

- Any related AE, worsening of health status or intercurrent illnesses that, in the opinion of the investigator, requires discontinuation from study vaccine
- The participant becomes pregnant
- Unblinding (other than scheduled unblinding) on the participant level that, in the opinion of the sponsor, would compromise the integrity of the data
- Anaphylactic reaction following vaccination, not attributable to causes other than vaccination

- SAE or other potentially life-threatening (Grade 4) event that is determined to be related to study vaccine
- Chronic (>14 days) or recurrent use of systemic corticosteroids and administration of antineoplastic and immunomodulating agents or radiotherapy
- Withdrawal of consent/assent to receive further study vaccination (second vaccination of the 2-dose regimen)
- Participant receives any experimental medication (including experimental vaccines other than the study vaccine) or receives an anti-COVID-19 vaccine or treatment
- Participant previously experienced TTS or heparin-induced thrombocytopenia (HIT), GBS or MIS-C.
- Per the implementation of Amendment 1, the participant has a history of CLS.

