- Adolescent (12 to 17 years of age) participants will be provided a pulse oximeter at baseline to measure blood oxygen saturation and pulse rate during a COVID-19 episode (see Section 1.3.3).

- h. Pulse/heart rate, preferably supine systolic and diastolic blood pressure, respiratory rate, and body temperature. Pulse/heart rate measurements should be taken preceded by at least 5 minutes of rest (if feasible) in a quiet setting without distractions (eg, television, cell phones). Vital signs measurements are recommended before blood sampling. Body temperature will be measured preferably orally (routes to be recorded in the eCOA).
- i. Rapid serological test for anti-SARS-CoV-2 antibody will collect blood from a small puncture in the finger (finger-prick test at screening).
- j. If a rapid serologic test is completed ≤ 3 days before vaccination, a repeat test is not required on Day 1
- k. Investigator must check for clinically significant acute illness or body temperature $\geq 38.0^{\circ}\text{C}/100.4^{\circ}\text{F}$ at the time of vaccination. If any of these events occur at the scheduled time for vaccination, the vaccination can be rescheduled as long as this is in agreement with the allowed windows. If the vaccination visit cannot be rescheduled within the allowed window or the contraindications to vaccination persist, the sponsor should be contacted for further guidance. The investigator should also check if any other reasons, as listed in Section 7.1, have been met and would prevent further study vaccination.
- l. For participant of childbearing potential only.
- m. Whole blood samples will be used for complete blood cell count, including platelet count (hematology, see Section 10.2, Appendix 2), in a local laboratory or substitute for local laboratory, depending on local feasibility towards turnaround time of sample processing. Results should be available within 72 hours. The division of volumes between whole blood, plasma and serum is described in the laboratory manual. Serum and plasma are to be stored centrally for future testing to evaluate the impact of any potential thromboembolic events. Samples can also be tested (centrally) for anti-PF4 antibodies and platelet activation assay (if HIT/PF4 is positive). Unused samples may be used for immunogenicity testing.

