5.2. Exclusion Criteria

Any potential participant who meets any of the following criteria will be excluded from participating in the study:

1 Participant has a clinically significant acute illness (this does not include minor illnesses such as diarrhea or mild upper respiratory tract infection) or temperature $\geq 38.0^{\circ}\text{C}$ (100.4°F) within 24 hours prior to the planned first dose of study vaccine; randomization at a later date is permitted at the discretion of the investigator and after consultation with the sponsor.

2 Participant has a history of malignancy, bone marrow transplant, or solid organ transplant within 5 years before screening.

3 Participant has a known or suspected allergy, history of anaphylaxis, or other serious adverse reactions, related to vaccines or their excipients (including specifically the excipients of the study vaccine) (refer to the [IB Ad26.COV2.S 2022](#)).

4 Use of systemic corticosteroids at an immunosuppressive dose (treatment duration more than 14 days for one course or recurrent use) within 6 months before administration of study vaccine and during the study

Note: For corticosteroids, this means prednisone, or equivalent, ≥ 20 mg/day. For participants below 45 kg, the dose is above 1 mg/kg/day.

Ocular, topical, or inhaled steroids are allowed.

Non-immunomodulator treatment is allowed as well as steroids at a physiologic dose.

5 Participants with a history of illness or with an ongoing illness that, in the opinion of the investigator, may pose additional risk to the participant if he/she participates in the study.

6 Criterion modified per Amendment 1:

6.1 Any serious, chronic, or progressive disease (eg, diabetes, cardiac disease, hepatic disease, progressive neurological disease or seizure disorder; autoimmune disease, AIDS infection, blood dyscrasias, bleeding diathesis, signs of cardiac or renal failure, or severe malnutrition).

Note: Stable and medically well controlled chronic conditions (defined as no change in medication over the past 6 months, other than weight-based adjustments for normal growth) are allowed per investigator discretion such as:

- Diabetes: HgbA_{1c} <7% and/or no episodes of diabetic ketoacidosis in the past 6 months.
- Cardiac disease (eg, arrhythmias, heart murmurs): Repaired cardiac defects without residual lesions. No surgery or intervention (eg, trans catheter procedures) in the past 6 months and no anticipated procedures for 6 months post first vaccination.

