Antipyretics are recommended post-vaccination for symptom relief as needed. Prophylactic antipyretic use is not encouraged, however, in some instances, it could be considered for participants only in special circumstances.

Chronic (>14 days) or recurrent use of systemic corticosteroids^a, at immunosuppressive doses and administration of antineoplastic and immunomodulating agents or radiotherapy are prohibited during the study and within 6 months before the planned administration of the first dose of study vaccine. If any of these agents are indicated in a disease setting, these must take priority over the study vaccine.

Refer to Section 5.2, Exclusion Criteria for further details of prohibited therapy.

The sponsor must be promptly notified of any instances in which prohibited therapies are administered. The participant should remain in the study but receive no further study vaccination. Depending on the time of the occurrence, a participant who receives a prohibited concomitant medication will not be included in the immunogenicity analyses.

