6.8. Study Vaccination Pausing Rules

The principal investigator (PI) and the study responsible physician/scientist (SRP/SRS) will monitor safety in a blinded manner, including the study vaccination pausing rules. If a study vaccination is considered to raise significant safety concerns (and a specific set of pausing criteria have been met), further vaccination of participants will be paused. The concerned data will be reviewed by the IDMC, after which the IDMC will recommend whether the pause can be lifted or not, or whether other steps are needed.

The IDMC will review blinded data first but has the right to request the randomization codes and review unblinded data if deemed necessary. The IDMC will make recommendations regarding the continuation of the study to the sponsor study team. The sponsor study team will communicate conclusions regarding study continuation to the investigator, the IEC / IRB, and applicable health authorities as appropriate.

After the first IDMC meeting triggered by the occurrence of a given pausing rule, the IDMC will convene thereafter for each additional participant meeting that pausing rule.

The occurrence of any of the following events will lead to a pause in further study vaccination (once the pause is lifted, the decision regarding subsequent vaccination [if applicable] will be

^a Note: Ocular, topical, or inhaled steroids are allowed. Non-immunomodulator treatment is allowed as well as steroids at a physiologic dose.

assessed on a case by-case basis, upon discussion between sponsor and investigator). Laboratory abnormalities noted below refer to cases where the study-site personnel perform laboratory safety testing for investigation of an AE.

1. Death of a participant, considered related to study vaccine or if the causal relationship to the study vaccine cannot be excluded; OR

Note: All cases of death will be sent to IDMC for information. Upon their review, IDMC may then decide whether a study pause is required.
2. One or more participants experience an SAE or a Grade 4 (solicited or unsolicited) AE or a persistent (upon repeat testing) Grade 4 laboratory abnormality that is determined to be related to study vaccine; OR
3. One or more participants experience anaphylaxis or generalized urticaria, clearly not attributable to other causes than vaccination with study vaccine; OR
4. One or more participants experience MIS-C which is assessed as at least possibly related to study vaccine; OR

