Study visits, other than screening and visits at which study vaccination is scheduled, may take place at the participant's home by site staff or a trained and delegated HCP if there are travel restrictions in case of an ongoing pandemic and if allowed by local regulations. The PI continues to be responsible for reviewing all protocol-related assessments. If home visits are not allowed by local regulations, procedures and activities may be done by other methods where possible (such as telephone or video conferencing).

Visit Windows

Visit windows are provided in Section 1.3. The participant should be encouraged to come on the exact day planned and use the visit window only if absolutely necessary.

The timings of the post-vaccination visits will be determined relative to the actual day of the corresponding vaccination. If a participant misses a vaccination, the post-vaccination visits will be scheduled using the date that the vaccination was scheduled to take place.

If a vaccination window is missed due to a study pause (see Section 6.8), efforts will be made to still vaccinate the participant, even if out of window. The timings of the post-vaccination visits will be determined relative to the actual day of the vaccination, unless they would overlap with other scheduled visits, in which case the sponsor should be contacted and a case-by-case assessment is to be agreed upon.

Screening

Screening will be performed within 28 days prior to the first study vaccination or on the day of vaccination. If screening is performed on the day of vaccination, Visit 1 and Visit 2 will both occur on Day 1. Screening must be completed, and all eligibility criteria must be fulfilled prior to randomization and vaccination.

Screening may be conducted in part via a sponsor- and IRB/IEC-pre-approved non-study-specific screening consent process, but only if the relevant pre-screening tests are identical to the per protocol screening tests and are within 28 days prior to first vaccination. However, no study-specific procedures, other than these pre-approved pre-screening assessments, will be performed until the participant has signed the study-specific ICF. Participants who test positive on the molecular test or the serological test (antibodies) will be informed of the result by the study site staff. The study-specific ICF date will be entered into the eCRF. The non-study-specific ICF will be considered source data.

Sample Collection and Handling

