6.3. Appendix 3 The Per Protocol Immunogenicity population

The Per Protocol Immunogenicity population will include all randomized and vaccinated participants for whom immunogenicity data are available excluding participants with major protocol deviations expected to impact the immunogenicity outcomes and occurring on Day 1 or before.

In addition, samples obtained from participants will be excluded from the analysis set:

- a- after major protocol deviations expected to impact the immunogenicity outcomes and occurring after Day 1,
- b- after missed vaccinations,
- c- on or after natural SARS-CoV-2 infection (if confirmed by molecular testing or non-S-ELISA [or equivalent assay]) occurring during the study after randomization (if applicable),
- d- after other SARS-CoV-2 vaccination outside the study, or
- e- outside pre-defined time windows (Section 5.1.4).

In terms of derivation, the samples to consider for analysis on Per Protocol Immunogenicity must meet the following criteria:

Subject level

- **Crit1:** Must be randomized
- **Crit2:** Must be in FAS

- **Crit7:** No major protocol deviations with impact on immunogenicity on or before day 1 excluding Deviation Categories '85 for sample not in window', '87 for sample not stored properly'

Subject data level

Subject data to be excluded on and after the date of any of the following events:

- **Crit11:** seropositive post-Baseline by N-ELISA (value>LLOQ), if seronegative at baseline (as defined in Section [5.8.4](#))
- **Crit13:** SARS-CoV-2 infection occurring on or after Day 1
- **Crit20:** Major protocol deviations with impact on immunogenicity after day 1 except for deviation categories '85' or '87', which includes
 - **Crit21:** post SARS-CoV-2 viral vaccination outside the study occurring after Day 1
 - **Crit22:** Vacc 2 not in D57 +/- 8 days
 - **Crit23:** no Vacc 2, then exclude samples where the sample date>Day57+8.
 - **Crit24:** Vacc 3 not in D184 +180/-30 days post vacc1 – Groups 1, 2, 3
 - **Crit25:** no Vacc 3 (within 180 days post Day 184), then exclude samples where the sample date>Day184+30 – Groups 1, 2, 3

Vacc 2 refers to the 2nd dose of the primary regimen

Vacc 3 refers to booster

Sample level

Samples to be excluded on the date of deviation for '85' or '87' events:

- Crit30: major protocol deviations with impact on immunogenicity deviation categories '85' or '87', that is
 - **Crit31:** D1 sample not in window
 - **Crit32:** D29 sample not in window

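### Section 7.1 stops all further vaccination for any chronic or recurrent systemic steroid course, without the dose limit that Section 6.7 and exclusion criterion 4 apply to the same therapy during the study

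*Protocol*

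**What the plan says.** Section 7.1 lists reasons for withholding study vaccination. Participants who meet one get no more doses but stay in follow-up. One reason is "Chronic (>14 days) or recurrent use of systemic corticosteroids and administration of antineoplastic and immunomodulating agents or radiotherapy". The bullet has no dose threshold, footnote or cross-reference.

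Two other places govern the same therapy in the same period:

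- **Section 6.7** restricts chronic or recurrent systemic steroids only "at immunosuppressive doses and administration of antineoplastic and immunomodulating agents or radiotherapy are prohibited during the study". Its footnote adds: "Non-immunomodulator treatment is allowed as well as steroids at a physiologic dose". The section states its own consequence for a prohibited therapy: the participant remains in the study and is not vaccinated again.
- **Exclusion criterion 4 (Section 5.2)** covers the 6 months before vaccination and also the study itself. It concerns "Use of systemic corticosteroids at an immunosuppressive dose (treatment duration more than 14 days for one course or recurrent use". Its note sets the limit at prednisone or equivalent of at least 20 mg/day and continues: "For participants below 45 kg, the dose is above 1 mg/kg/day".

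Footnote k of both Schedules of Activities (Sections 1.3.1 and 1.3.2) sends sites to the Section 7.1 list before vaccination: "The investigator should also check if any other reasons, as listed in Section 7.1, have been met and would prevent further study vaccination".

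**The concern.** The Section 7.1 bullet closely follows the Section 6.7 sentence but drops its dose qualifier. The mandatory stopping rule is therefore wider than the restriction it restates, and no reason is given for the difference. For immunosuppressive doses the bullet adds nothing, because Section 6.7 already ends vaccination for prohibited therapy. Its only extra effect on steroid users falls on courses below the threshold.

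Two things are at stake. An adolescent could lose an active dose without a stated safety reason: dose 2 in Groups 4-6, the booster in Groups 1-3. The missed dose would also trigger PPI exclusions that the steroid course alone would not. Section 6.7 removes participants from immunogenicity analyses for prohibited medication, and a below-threshold course is not prohibited. In Groups 4-6 the lost samples include Day 71, which is 14 days after dose 2 and the timepoint on which the 2-dose regimen is judged.

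**Working it through.** The plan states no figure on this point, so there is none to reproduce. The check compares the three rules and then counts the samples affected.

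**Rules side by side**

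| | Exclusion 4 | Section 6.7 | Section 7.1 |
|---|---|---|---|
| Applies during the study | yes | yes | yes |
| Duration | over 14 days, or recurrent | over 14 days, or recurrent | over 14 days, or recurrent |
| Dose limit | immunosuppressive, defined | immunosuppressive | none |
| Physiologic dose | allowed | allowed (footnote) | not mentioned |
| Further vaccination | not stated | none, if prohibited | none |

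**Test case (assumed).** A 50 kg participant takes prednisone 15 mg/day for 15 days after dose 1. The weight is not below 45 kg, so the limit is 20 mg/day. Since 15 < 20, criterion 4 and Section 6.7 do not apply. Since 15 days > 14 days, Section 7.1 does, and further doses are withheld. The result is the same at 5 mg/day. A single course of 14 days or less triggers none of the three rules, and ocular, topical and inhaled steroids are not systemic.

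**PPI cut-offs (SAP Section 6.3)**

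- Crit23, all groups: "no Vacc 2, then exclude samples where the sample date>Day57+8". Cut-off = 57 + 8 = Day 65.
- Crit25, Groups 1-3, no booster within 180 days of Day 184: samples after Day 184 + 30 = Day 214 are dropped.

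The target days can be used because of the visit rule in Protocol Section 8: "If a participant misses a vaccination, the post-vaccination visits will be scheduled using the date that the vaccination was scheduled to take place".

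**Scheduled humoral samples (Sections 1.3.1 and 1.3.2)**

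- Groups 4-6: Days 1, 29, 57, 71, 240 (5 days).
- Groups 1-3: Days 1, 29, 57, 71, 184, 198, 366 (7 days).

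**Loss per affected participant, at target days**

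| Group and start of course | Doses withheld | Days after cut-off | Lost from PPI |
|---|---|---|---|
| 4-6, between doses | active dose 2 | 71, 240 (> 65) | 2 of 5 |
| 1-3, between doses | placebo and booster | 71, 184, 198, 366 (> 65) | 4 of 7 |
| 1-3, after Day 57 and before the booster | booster | 366 (> 214) | 1 of 7 |

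The Day 29 sample is kept in every row. With 50 participants planned per group, each case in Groups 4-6 removes 1/50 = 2% of that group's planned Day 71 data.

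**The case against.** The strongest reply is that nothing conflicts in operation. Section 6.7 says what is prohibited and Section 7.1 says when to withhold vaccine. The second may be stricter than the first, and a site that withholds under Section 7.1 breaches nothing. The stricter rule is cautious, and Section 7.1 invites sites with questions to contact the sponsor. That is true, but the protocol nowhere presents the wider rule as intended, and a site reading a clear bullet has no question to raise.

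Second, the affected set is very small. Inclusion 5 and exclusions 6.1 and 8.1 remove most steroid users at entry, so a case needs a new long or recurrent low-dose course after dose 1. Some such participants could be withheld anyway under the intercurrent-illness bullet. This stands and limits the size of the point. That other bullet, however, leaves the decision to the investigator, and the steroid bullet does not.

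Third, only physiologic dosing is expressly allowed. A course of 15 mg/day is below the defined limit, but the documents do not show it to be physiologic. This also stands: such a course is not prohibited, rather than expressly allowed.

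Fourth, the Groups 1-3 counts are less firm than they look. The general PPI definition also excludes samples taken after missed vaccinations, and the post-booster window cannot be checked without a booster date. Day 198 could therefore be lost too, making 2 of 7. Section 4.4 lets Groups 1-3 participants without a booster complete at 6 months after active vaccination, so Days 198 and 366 may not be collected. These points qualify the Groups 1-3 counts but not the Day 71 loss in Groups 4-6.

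**Conclusion.** The concern holds. Section 7.1 has no dose limit, the two rules covering the same therapy during the study do, and the Schedule of Activities makes Section 7.1 the list checked before vaccination. Followed literally, it withholds dose 2 or the booster for a course the protocol does not prohibit.

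The effect is narrow. The consequence that matters most is Day 71 in Groups 4-6. In Groups 1-3 the withheld second dose is placebo and the Day 29 selection sample is kept, so the cost there is the booster and its follow-up data. Immunogenicity analyses on the full analysis set would still include samples that were collected. The counts assume target visit days, continued sampling after a missed dose and, for the 1 of 7, Crit25 alone. The documents give no expected frequency. No sample size, precision or operating figure changes. The wording should be corrected, but the point does not threaten the trial's conclusions.

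**What to change.** In the Section 7.1 bullet, after the reference to systemic corticosteroids, insert *at immunosuppressive doses, as defined in exclusion criterion 4*. Add that physiologic doses and ocular, topical or inhaled steroids are allowed, and leave the rest of the bullet unchanged. If the sponsor does want the wider stopping rule, Section 7.1 should say so with a reason, and Section 6.7 should point to it.

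The cost is one line of protocol wording. The definition already exists, and the design, sample size and analysis do not change.

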7.2. Participant Discontinuation/Withdrawal From the Study

A participant will be withdrawn from the study for any of the following reasons:

- Lost to follow-up
- Withdrawal of consent or assent from the study
- Death
- Repeated failure to comply with protocol requirements

When a participant withdraws before study completion, the reason for withdrawal is to be documented in the eCRF and in the source document.

For those participants who are unable to continue participation in the study up to the last planned study visit, but for whom consent or assent is not withdrawn, an early exit visit will be conducted as soon as possible. Participants who wish to withdraw consent or assent from participation in the study will be offered an optional visit for safety follow-up. This includes the safety assessments of the early exit visit (no blood sampling for immunogenicity).

Withdrawal of Consent or Assent

A participant declining to return for scheduled visits does not necessarily constitute withdrawal of consent or assent. Alternate follow-up mechanisms that the participant agreed to when signing the consent or assent form apply as local regulations permit.

